We will also track patients who did not send the kits in (via EPIC reports). These patients will not undergo surveillance because they will not have

completed the required screening component. If three calls are made and they do not use the kits, they will be considered lost to f/u. This will be important information when results are reported.

VII.D.23 *Will this information be shared with anyone outside the UI research team members?*
No

VII.D.25 *After the subject agrees to participate (signs consent), are there any screening procedures, tests, or studies that need to be done to determine if the subject is eligible to continue participating?*
Yes

VII.D.26 *List and describe screening*
As described in VII.D.22, the patient must use and return the preoperative swab kits. Three reminders will be provided. If they do not complete the initial screening process, they will be considered lost to f/u. Information required to meet inclusion criteria will be self evident (age which is in the chart, surgical service line which is already known...they are in the randomized line, and need for general/regional anesthesia (this is decided by the procedure).

VII.D.27 *Discuss how much time a potential subject will have to agree to consider participation and whether or not they will be able to discuss the study with family/friends before deciding on participation.*
The patient will be seen in clinic, PAT, or on the floor/ICU as part of their visit. The initial time to decide will be limited by the study visit, as a preoperative order must be placed. However, they will be able to decline at any point down the road as previously described, including simply deciding not to use and return the ordered kit.

VII.D.28 *How long after the subject agrees to participate do study procedures begin?*
Our goal is to focus on a 10-day window prior to surgery so that the kit can be shipped (two days), received (two days), processed (up to 2 days), and in the treatment group, treated for 2-4 days.

VII.D.29 *Provide a description of the enrollment and consent process for adult subjects*

- *Describe each study population separately including control population*
- *Include when recruitment and consent materials are used*

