- *Use 3rd person active voice "The Principal Investigator will identify subjects. For example, the principal investigator will identify potential subjects, the study coordinator will discuss the study with subjects over the telephone and schedule the first study visit, etc..."*
- *Describe the steps that will be taken by the research team to minimize the possibility of coercion or undue influence during the consent process*

We will be attempting to capture all patients that meet inclusion criteria which could include patients seen and consented in the clinic, seen and consented on the hospital floor, intensive care units (inpatient surgery), or pre-anesthesia testing (PAT). Any patient meeting inclusion criteria that the surgeon obtains surgical consent for could be captured and tracked by the preoperative order.

Preoperative signed and held orders for preoperative swab kits will populate a list in EPIC for the PI ([name]). This list will be filtered by type of surgery, surgeon, and date of surgery within 10 days. Members of the research team will send out the kits after approval from the PI. Either treatment or control kits will be sent based on the service line, which will be linked by the kit number, and this will determine delivery of usual care or the treatment bundle on the day of surgery.

Before a kit is sent to the patient, a new signed and held order will be placed and associated with the kit number (specific to the kit sent to the patient) which will update the EPIC list with the kit number. The kits sent by the patient to RDB will be accomplished by a prepaid mailer. Patients will use and return the kits to RDB.

RDB will receive and process the kits. RDB will track the returned kit numbers and provide a list to [name]. [name] will complete the signed and held orders for patients in the Clarity report that returned kits for processing.

The completed POC will again update the Clarity report. The research assistants will work the list to select 2 patients with completed POC orders, treatment and control, for OR PathTrac Observation each day.

The assistants will confirm 1st patient consent. Once confirmed, an OR PathTrac Kit will be ordered in EPIC, a consent confirmed box checked in the RDB microEMR, and the preoperative swab and OR PathTrac kit numbers entered along with baseline patient demographic information.

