Preoperative swab kit orders will track informed, written consent and will populate a list in EPIC for the PI ([name]) that will be sorted by type of surgery and filtered (at the top of the list) by patients with orders for the kit that are actually booked for surgery within 10 days of the current date. That list will be used by [name] to send kits to patients for preoperative swabbing and if in the treatment group, decolonization with Povidone iodine. Before sending, a new signed and held POC preoperative swab kit order will be placed and associated with the kit number. The kits will be sent by the research team to the patient along with a prepaid mailer. The kit will include 3 swabs (nasal, axillary, and groin), preprinted instructions for use, and an insert briefly summarizing the study for a reminder (see attached documents). The patient will follow the kit instructions and send the kit to RDB for processing.

RDB will process the samples and enter the results into the software platform. RDB will send a list of kit numbers received to [name]. [name] will complete the signed and held order in EPIC for those received. This will create an ICON indicating complete. The complete ICON will guide OR PathTrac Surveillance, where a treatment and control patient are selected each day, as geographically dispersed as possible in the OR.

Patients in treatment lines with completed orders who are selected for surveillance will receive the treatment bundle (see below). Patients in usual care lines with completed orders who are selected for surveillance will receive usual care. All second patients in the observational pairs described below will receive usual care. Only the first patient in a treatment pair will receive the bundle (The goal is to examine the impact of an evidence-based bundle in preventing spread of bacteria from one patient to another).

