This will involve use of a sterile ESwab to obtain nasal, axillary, and inguinal swabs. Nasal: the swab is to be inserted into each nares no more than 3/4 of an inch and rotated 360 degrees 10 times. Axillary: the swab will be applied to the middle of the armpit, pressed firmly against the skin, and rotated 10 times. Inguinal: the swab will be applied to the inguinal crease, pressed firmly against the skin, and rotated 10 times. After collection, each swab will be inserted into the collection medium (Aimes transport medium), the applicator stick snapped off as directed, and the cap placed on the tube to seal the contents.

Treatment Bundle:

Decolonization: Each patient in the treatment group will receive Povidone iodine treatment for their nose and potentially their surgical site on the day of surgery in the Day of Surgery Admissions(DOSA) area. The surgical team will approve and guide the application of the povidone iodine to the likely surgical incision site(s) or it will not be placed. The application of the povidone iodine to the inside of the nose will be guided by a member of the research team. 2% Chlorhexidine body Wipes are currently used in UIHC Day of Surgery Admission (DOSA) to help disinfect patient skin before surgery

and we will make sure that treatment patients are properly administered these wipes and educated on their use.

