 - Improved environmental cleaning: Environments (OR and ward) affected by high-risk S. aureus transmission events will be mapped by surveillance and addressed by automated reporting to the anesthesia workroom supervisor. This will trigger improvements in routine (standard cleaning using quaternary ammonium compound and micro cloth followed by a surface disinfection wipe) and terminal [improved routine technique followed by employment of robotic cleaning (Ultraviolet light)] cleaning.
- Fatigue mitigation: The team will use surveillance to continually monitor the impact and fatigue of the proposed interventions as conveyed by failure mode analysis of transmission dynamics involved clonal S. aureus transmission.

XI.2

Provide the rationale or power analysis to support the number of subjects proposed to complete this study.

Statistical Analysis: The unadjusted primary intention to treat analysis will compare the proportion of clonally-related S. aureus transmission events occurring in treatment vs. control perioperative (preoperative, intraoperative case pair, and postoperative) observational units across the 6 randomized service lines using the Chi squared test. We will assess for balance for variables known to be associated with intraoperative

transmission (case, duration > 2 hours, and discharge location). In the case of imbalance, we will use multivariate techniques to further explore the treatment effect using a generalized linear models approach.

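### First patients are observed only if they return an arm-designated kit mailed after allocation, so the comparison labelled intention to treat is a comparison of kit-returners

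*Protocol*

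**What the plan says.** The order of events in the protocol is as follows.

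- **Allocation.** The service line is the unit of randomisation (VI.13). When a patient is screened the line is already known: "they are in the randomized line" (VII.D.26).
- **Mailing.** After consent, "Either treatment or control kits will be sent based on the service line" (VII.D.29). The kit number then governs whether the bundle or usual care is given on the day of surgery.
- **Condition.** Under VII.D.26, "the patient must use and return the preoperative swab kits". Up to three reminders are given.
- **Consequence.** "If they do not complete the initial screening process, they will be considered lost to f/u" (VII.D.26). The screening-log section adds: "These patients will not undergo surveillance because they will not have" completed that step (VII.D.22). Only patients whose order is marked complete can be chosen for the daily treatment and control observations (VI.15, VII.D.29, VII.E.6).
- **Declining.** VII.D.27 accepts not using and not returning the kit as a way to leave the study.
- **Analysis.** "The unadjusted primary intention to treat analysis will compare the proportion" of clonally related transmission events between arms (XI.2).

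The SAP defines no intention-to-treat set. It compares enrolled with eligible patients, by surgeon, on ASA score above 2 and on sex, and states that no primary or secondary outcome data were missing.

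**The concern.** Returning the kit is something the patient does after the line's arm is fixed, and it decides whether a primary outcome exists at all. An analysis restricted in this way does not include everyone allocated and consented, whatever it is called.

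Two consequences follow. First, the result describes first patients who complete a mailed self-swab procedure, plus the patients who follow them. Second, if the two mailings ask for different things, different kinds of patient may drop out of each arm, and a difference in transmission could appear, or be hidden, with no bundle effect behind it.

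The protocol does not settle whether the mailings differ. One part of VII.E.6 has the research team "send kits to patients for preoperative swabbing and if in the treatment group, decolonization with Povidone iodine". VII.D.28 allows for a treatment period of some days before surgery in the treatment group. The Treatment Bundle part of VII.E.6 says "Each patient in the treatment group will receive Povidone iodine treatment" on the day of surgery in the admissions area.

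**Working it through.** **1. The plan's own figures.** For 500 patients per arm and 40% against 28%, XI.2 states 98% power with no variation between lines. With a two-sided 5% pooled z test:

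- SE under no difference = √(2 × 0.34 × 0.66 / 500) = 0.0300
- SE under the alternative = √((0.40 × 0.60 + 0.28 × 0.72) / 500) = 0.0297
- Power = Φ((0.12 − 1.96 × 0.0300) / 0.0297) = Φ(2.06) = 98.0%

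The figure reproduces. It concerns precision among those analysed and is silent on who they are.

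**2. Planned loss.** XI.2 expects 2,800 consents to yield 2,000 usable patients, that is 1,000 pairs.

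- Spread evenly over all consented patients: 800 / 2,800 = 28.6%
- All falling on first patients: 2,800 − 1,000 = 1,800, and 800 / 1,800 = 44.4%

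Both cover every cause that XI.2 names: non-compliance, first patients changing their mind, and refusal by the second patient, which excludes the pair and so also removes a consented first patient. Neither is a rate of kit non-return, which the documents do not give.

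**3. Sensitivity, on assumed values.** Let p = 40% be the transmission risk among all consented first patients in both arms, so there is no true effect. Let d be the share not returning the kit and r the risk of non-returners relative to returners. The rate seen among returners is

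x = p / ((1 − d) + d × r)

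Example: d = 0.35 and r = 1.5 give 0.40 / 1.175 = 34.0%; d = 0.22 and r = 1.5 give 0.40 / 1.11 = 36.0%.

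| d, treatment / control | r, treatment / control | Treatment | Control | Spurious difference, points | Rejection rate |
|---|---|---|---|---|---|
| 28.6% / 28.6% | 1.5 / 1.5 | 35.0% | 35.0% | 0.0 | 5% |
| 35% / 22% | 1.5 / 1.5 | 34.0% | 36.0% | 2.0 | 10% |
| 40% / 17% | 1.5 / 1.5 | 33.3% | 36.9% | 3.5 | 22% |
| 28.6% / 28.6% | 1.5 / 1.0 | 35.0% | 40.0% | 5.0 | 37% |

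Differences come from unrounded rates. Rejection rates use the pooled z test with 500 per arm and ignore clustering by line. Swapping the arms reverses the sign. The first row shows that equal return by the same type of patient gives no bias between arms. The last shows that equal return alone is not enough. For scale, the planned effect is 12 points.

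**4. Who is selected.** The kit condition applies directly to first patients. Second patients receive no swab kit (VII.E.6), but they enter only behind a first patient who returned one.

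**The case against.** The plan does not ignore non-returners. It gives three reminders, tracks non-return through EPIC and says this will matter when results are reported (VII.D.22, VII.D.26), and logs age and sex by line expressly to look for selection bias (VII.D.22). The SAP adds its check on ASA and sex. This stands, and part of what is asked for below is already collected. But none of it restores intention to treat. Age, sex and ASA do not measure colonisation or transmission risk, and no comparison of kit return by arm is specified. The SAP's statement on missing data can hold only if unobserved non-returners lie outside the analysis set.

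A heavier treatment mailing is also not established. The contents listed in VII.E.6 (three swabs, instructions, an insert) do not differ by arm, the treatment or control designation may be no more than a tracking label, and VII.E.1.a says some subjects are blinded. This stands too: the difference is possible, not shown.

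A reader might infer that non-returners should simply be observed as well, because patient swabs are repeated after induction and two of the four windows in XI.2 need no mailed kit. The documents do not support that remedy. VII.D.27 treats non-return as a way to decline, VII.E.6 ties the bundle to completed orders, and the primary outcome includes the preoperative period. It could also bias the comparison. Assume four equal, independent windows, 40% with any transmission, no effect, and return of 65% in treatment against 80% in control. Two windows detect 1 − √0.60 = 22.5%. Treatment then shows 0.65 × 40 + 0.35 × 22.5 = 33.9% and control 0.80 × 40 + 0.20 × 22.5 = 36.5%, a spurious 2.6 points.

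**Conclusion.** The point holds as a fault of labelling and scope, with a risk of bias attached. The primary comparison is not intention to treat. It compares first patients who returned a kit, and the patients who followed them, by allocated line.

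The size and direction of any bias are unknown. The 2 to 5 points in the non-zero rows of the sensitivity table rest wholly on assumed return rates and risk ratios, and the bias is zero if return and the type of non-returner match across arms.

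Two stronger readings are tempting. One is that the arms are in fact imbalanced, so that an observed benefit would be an artefact; nothing in the documents shows different return by arm. The other is that 29% to 44% of first patients fail to return kits; those figures are total planned loss from all causes under two assumptions about where it falls.

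**What to change.** 1. Make the kit that must be returned, its instructions and its reminders identical in both arms. Keep any arm-specific material separate from the return step and after it. Reconcile VII.D.28 and the two parts of VII.E.6 on what the mailing contains; which statement is right is for the sponsor to decide.
2. In XI.2, replace the intention-to-treat label with: patients who returned a kit, analysed by allocated line (modified intention to treat). Carry the same definition into the SAP and limit the conclusion to that group.
3. Report counts consented, sent a kit, returning it, selected and paired, by arm and by line. Compare returners with non-returners within each arm on the characteristics already logged.

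Items 2 and 3 cost wording and tabulation, mostly from records the plan already keeps. Item 1 costs little if the mailings are already alike. If they are not, a separate later mailing has to fit the ten-day window in VII.D.28, whose listed steps at their longest already fill it (2 + 2 + 2 + 4 = 10 days). Surveillance slots and staffing do not change. The price is a narrower claim.

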We will be attempting to capture all patients that meet inclusion criteria which could include patients seen and consented in the clinic, seen and consented on the hospital floor, intensive care units (inpatient surgery), or pre-anesthesia testing (PAT). Any patient meeting inclusion criteria that the surgeon obtains surgical consent for could be captured. Poster reminders will be placed in the clinics, on the ward, and PAT. The study consent forms will be attached to the surgical consent forms. Surgical providers obtaining surgical consent will obtain study consent when possible. This will otherwise be executed via our research team via pager. Preoperative kit orders will be completed by surgical providers or physician study team members when needed. The signed and held order will populate a list in EPIC for the PI ([name]) that will be filtered by type of surgery, surgeon, and date of surgery within 10 days. It will include the patient medical record number, address/phone number, and an icon indicating the POC signed and held order. [name] will work the list to send ordered kits to patients. [name] will enter a new signed and held order for the kit and will associate the assigned kit number with the order, which will create a new ICON indicating ordered kit sent to patient. This will also update the Clarity report in EPIC with the kit number in addition to the other previously mentioned fields. The patient will receive the kit along with a reminder for why they received the kit (see attached in miscellaneous), use the kit (up to 3 reminders will be provided by [name] study team), and RDB will receive and process the kits. Patients will use a prepaid mailer to send the kits to RDB which will have the RDB address in the send and return fields so that patients are not revealing their identity to RDB (process okay per USPS). RDB will send returned kit numbers to [name] daily. [name] will complete the signed and held orders for patients in the Clarity report that returned kits for processing. The completed POC will generate another ICON indicating received and processed and will again update the Clarity report. The research assistants will work the list to select 2 patients with completed POC orders, treatment and control, for OR PathTrac Observation each day. The assistants will confirm 1st patient consent. Once confirmed, an OR PathTrac Kit will be ordered in EPIC which creates an ICON indicating consent confirmed, a consent confirmed box checked in the RDB microEMR will be placed (3 ways for tracking consents, the written document and two electronic confirmations), and the preoperative swab and OR PathTrac kit numbers entered into the microEMR along with baseline patient demographic information (OR room number and case number, surgery duration, date and time). Informed, written consent will be obtained from the second patient on the day of surgery (see attached consent for patient 2), an OR PathTrac Kit ordered, demographic information (see previous) entered into the microEMR, and surveillance completed. If the second patient does not provide consent for their samples, the pair will be excluded and recruitment continued to reach 1,000 pairs. Our prior experience and recent experience at the University of Iowa strongly suggests that patient refusal to provide written consent for intraoperative cultures will be a rare event. The assistant will then follow the 1st patient to the recovery area for sampling as previously described using the Ward Environment Surveillance (WES) kits. The WES kit number will be associated by the micro EMR to the other kit units. This

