- *Procedures include a confederate pretending to be another participant in the study.*
- *Participants will be told that the research includes completion of a particular task, when in fact, that task will not be administered.*
- *Study is designed to introduce a new procedure (or task) that participants are not initially told about.*
- *If yes, a waiver of informed consent must be requested under question IV.3.*

No

VII.E. Project Description (E)

VII.E.1 *Will subjects be randomized?*

Yes

VII.E.1.a *Will any subjects be blinded to which study arm they have been assigned?*

Yes

VII.E.1.b *Does the protocol permit telling subjects their treatment assignment at the end of the entire study?*

No

VII.E.1.d *Justify why subjects cannot be told what study arm they have been assigned. You will need to disclose to subjects in the consent document that they cannot receive this information.*

This is a quality improvement project protected by quality assurance.

VII.E.2 *Describe randomization scheme/assignment including ratio such as 1:1, 2:1 etc.*

The service lines have been previously described. These lines will be randomized 1:1 to treatment (bundle) and usual care. This randomization will be computer generated by RDB software.

VII.E.3 *Will any questionnaires, surveys, or written assessments be used to obtain data directly from subjects in this study?*

No

VII.E.5 *Does this project involve creating any audiotapes, videotapes, or photographs?*

No

VII.E.6 *Provide a detailed description in sequential order of the study procedures following the consent process - DO NOT cut and paste from the Consent Document.*

Describe study populations separately if they will be participating in different procedures - include CONTROL population if applicable.

DESCRIBE:

- *What subjects will be asked to do/what happens in the study (in sequential order)*
- *The time period over which procedures will occur*
- *The time commitment for the subject for individual visits/procedures*
- *Long-term followup and how it occurs*

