For surveillance in the OR for both treatment and control patients selected for observation, the observational unit will be a case pair. The first patient will have been previously consented. This will be confirmed by the research assistants. An OR PathTrac Kit will be ordered by [name] or another physician research team member once consent is confirmed. The OR PathTrac and preoperative swab kit numbers will be entered into the RDB microEMR along with patient demographic information. Source documents will include a screen shot of the microEMR page with kit numbers and demographics and the kit insert. The OR surveillance as directed by the OR PathTrac kit will be conducted. The kits will be transported to RDB by the research team for processing. RDB will enter the results into the software platform.

The second patient will be approached for informed, written consent by the research team. This document is distinct from the first patient consent, as the second patient will not receive Povidone iodine, will not be asked to use the preoperative swab kit, and will not undergo postoperative surveillance. Only the OR PathTrac kit surveillance (while they are in the OR) will be conducted for the second patient. Once written consent is obtained, an OR PathTrac Kit will be ordered by [name] or another physician research team member, the kit number associated with the first patient's preoperative swab kit and OR PathTrac kit numbers in the microEMR, and the demographic information entered into the microEMR as well. Source documents will include a screen shot of the microEMR page with kit numbers and demographics and the kit insert. The OR surveillance as directed by the OR PathTrac kit will be conducted. Kits will be transferred to RDB by the research team. RDB will process the kits and enter the results into the software platform. OR PathTrac kit orders electronically confirm obtained written consent.

The first patient will be followed to the recovery period. A ward environment surveillance (WES) kit will be used for surveillance. The kit will be associated to the above information in the microEMR as previously described. Ward (this is the recovery area, could be the intensive care unit, post anesthesia care unit, second stage recovery, a hospital floor, etc) surveillance will be conducted as directed by the kit. Kits will be

transferred to RDB by the research team. RDB will process the kits and enter the results into the software platform.

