- Biologic samples (blood draws, check swabs, saliva samples, tissue samples, etc.) - We will use IATA methods for bacterial transport/transfer. Patient swab samples will be stored and identified solely by the kit identification number used to obtain the swab. In the event that a patient subsequently develops an infection, patient cultures will be managed initially by the UIHC clinical lab in accordance with usual care. In addition, samples will later be transferred to RDB Bioinformatics. It is planned that long term storage of biological materials will be with RDB Bioinformatics at UI Bioventures.
 - Name - [name]
 - Title - Associate Professor
 - University Job Classification - FS12

X.5 *Do the confidentiality protections indicated above allow only members of the research team to access the data/specimens?*

No

X.6 *Describe*

RDB Bioinformatics is at UI Bioventures. Bacterial cultures will be de-identified (barcode) and demographic data linked to the barcode. Only bacterial culture data, OR date, surgical duration, OR room and case number, and kit numbers will be shared with RDB.

X.7 *Does your study meet the NIH criteria for a [Certificate of Confidentiality](#) or will you be applying for Certificate of Confidentiality?*

No

XI. Data Analysis

XI.1 *Describe the analysis methods you will use, including, if applicable, the variables you will analyze*

Enrollment/Randomization: Randomization is by the surgical line to treatment or control. The treatment bundle will include the improved RDB Bioinformatics S. aureus decolonization and screening processes described as above, as well as the previously described hand hygiene, environmental cleaning, and vascular care interventions. Active surveillance of bacterial transmission in the perioperative setting for both bundle and usual care groups will be used to drive activities that should further reduce the incidence of bacterial transmission. We will not disrupt processes that are already in place, and results will be entered into the medical record via standard laboratory resulting processes.

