Kits will be transported to RDB Bioinformatics laboratory for processing following sample acquisition. The dynamic surveillance software platform will guide proven, systematic phenotypic and genomic processing of collected samples in order to identify clonal transmission events occurring within and between operating room reservoirs in the observational unit (case pair). Guidance will be based on the strength of epidemiological-relatedness as follows: A transmission event will be defined as the presence of one or more isolates in a measured reservoir that was not present at case start. Transmission events within an observational unit will be further analyzed as directed by the RDB platform to identify clonally-related *S. aureus* transmission events.

The RDB Bioinformatics software platform will process transmission dynamics in order to continually summarize the epidemiology of *S. aureus* transmission. This information will be continually displayed in order to identify the most common reservoir of origin, the most common transmission locations (vectors), the most common mode of transmission (vertical or horizontal), and involvement of key portals of entry (stopcocks). To address strain characteristics, reports will focus on more pathogenic strains defined by the top 5 most transmissible, resistant, and virulent strain characteristics.

Automated analysis reports for overall transmission and for transmission of more pathogenic strains will be used by the infection control perioperative team to continually optimize the interventions affecting all patients in the treatment clusters as described further below. The platform will automatically quantify transmission events occurring in

treatment and control clusters such that involved in data collection and data entry will be blinded to the primary outcome.

All data will be analyzed by the statistician ([name]) at Dartmouth Hitchcock Medical Center who will not be involved in data collection.

Work flow: Monday-Friday only. Limited to patients that are seen in UIHC clinics. 1,000 case pairs: (500 treatment and 500 usual care) will be studied during the 2-year study period. This corresponds to one case pair in the “bundle” group and one case pair in the usual care group each day (5 days a week for 50 weeks each year). All patients will be followed for 90 days for infection development.

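### Arm-linked preoperative kits go to the same vendor that generates the allocation and calls the primary outcome, and nothing in the plan masks its laboratory to arm

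*Protocol*

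**What the plan says.** The relevant statements are spread over several protocol sections.

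- **Allocation (VII.E.2).** Service lines are randomized 1:1. "This randomization will be computer generated by RDB software".
- **Kits (I.4, VII.D.29).** The collection kits are RDB products, paid for by the grant. For the first patient's preoperative swabs, "Either treatment or control kits will be sent based on the service line, which will be linked by the kit number", and that link decides whether the bundle or usual care is given on the day of surgery. Patients mail the kits back, and "RDB will receive and process the kits".
- **Sample identity (X.4).** "Patient swab samples will be stored and identified solely by the kit identification number used to obtain the swab".
- **Linkage (VII.E.6, VI.15).** The second patient's OR kit is entered with "the kit number associated with the first patient's preoperative swab kit and OR PathTrac kit numbers in the microEMR". For the ward kit, "The WES kit number will be associated by the micro EMR to the other kit units".
- **Outcome (XI.1).** "Transmission events within an observational unit will be further analyzed as directed by the RDB platform", and the platform counts events by treatment and control cluster.
- **Protections.** Laboratory staff are confined to the laboratory part of the software (VII.B.23). The items shared with RDB are culture data, date, surgical duration, OR room and case number, and kit numbers; arm and service line are not listed (X.6). XI.1 says that data collection and entry are blinded to the primary outcome, and that the analysis is done by a statistician at another institution "who will not be involved in data collection".

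The SAP does not mention masking.

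**The concern.** The party that assesses the outcome is not a neutral laboratory. RDB's software is the device declared under study (VII.B.18-19), XI.1 counts RDB's own screening and decolonization processes as part of the bundle, and RDB is paid for the kits, the swab analysis and the platform analysis (I.4). In that position one expects an explicit statement that samples are read without knowledge of arm. The plan instead sends treatment or control kits, identified by number, into the laboratory that reads them.

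At stake is assessment bias in the only primary outcome. If choosing isolates, repeating tests or judging relatedness leaves any discretion, knowing the arm could shift the event count in one direction. The independent statistician cannot correct this, because that independence begins after the events have been called.

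**Working it through.** **Step 1: follow the arm information.**

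| Link | Held by | Source |
|---|---|---|
| Service line to arm | RDB software | VII.E.2 |
| Preoperative kit number to arm | Kit type, set by service line | VII.D.29 |
| Swab to kit number | The only identifier on the swab | X.4 |
| OR and ward kits to preoperative kit | microEMR | VII.E.6, VI.15 |
| Event counts by arm | RDB platform | XI.1 |

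Every link from allocation to outcome passes through one organisation. Since the platform counts events by treatment and control cluster, arm must be in the platform at some point.

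**Step 2: look for a break in the chain.** VII.B.23 restricts what laboratory staff can open in the software. It says nothing about what a kit or its number shows. X.6 withholds service line but shares kit number, OR room and date. With one treatment and one control pair a day (XI.1), identifying the arm of one pair identifies the other. The XI.1 blinding sentence seems to have lost its subject, so whom it covers is unclear, but what it withholds is the outcome. No statement masks the laboratory to arm.

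**Step 3: give a scale.** No stated figure depends on this point. The design inputs (XI.2) are 500 per arm, 40% against 28%, a difference of 12 points. They reproduce the plan's 98% power without line variation:

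- SE under no difference = √(2 × 0.34 × 0.66 / 500) = 0.0300
- SE under the alternative = √((0.40 × 0.60 + 0.28 × 0.72) / 500) = 0.0297
- z = (0.12 − 1.96 × 0.0300) / 0.0297 ≈ 2.06, so power ≈ 98.0%

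Let d be the share of treatment-arm events missed. The documents give no value; 5-10% is an assumption.

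- d = 5%: 0.05 × 28 = 1.4 points; 1.4 / 12 = 12%
- d = 10%: 0.10 × 28 = 2.8 points; 2.8 / 12 = 23%

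In general the share is d × 0.70 / 0.30 for a 30% relative reduction. The plan's other pair of rates (10.58% to 7.41%) therefore gives the same 12-23%.

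**Step 4: the same assumption with no true effect.** Both arms are then at 40%, with 500 per arm and a two-sided 0.05 test that treats patients as independent. Recorded treatment rates would be 38% (d = 5%) or 36% (d = 10%). The chance of a significant result rises from 5% to about 10% or 26%. Between-line variation is a separate matter and is left out.

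**The case against.** The strongest reply is that no one has shown the laboratory to be unmasked.

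- **Visibility of arm.** A reader might infer that the laboratory knows the arm of each sample. The documents do not support that. Nowhere do they say that the number or the returned package displays the arm. The VII.D.29 sentence can be read as hospital logistics, and VII.E.6 lists the same three swabs without distinguishing arms. This stands: the claim is only that the chain could reveal arm and that no masking is described.
- **Which samples.** Only the first patient's preoperative kit is described as arm-specific. OR and ward samples would be exposed through the microEMR link, or indirectly through room and date, and VII.B.23 restricts laboratory staff's access. This also stands.
- **Discretion.** XI.1 describes software-guided processing and automatic counting. That there is judgement at the bench is an assumption. Automatic counting does not, however, protect the culture and isolate-selection steps that feed it.
- **Size.** A reader might take 5-10% of 40%, that is 2-4 points or 17-33% of the target. At the design rates 40% is the control rate, and missing control events would shrink the difference. The 40% base applies to the treatment arm only if there is no true effect.
- **Cost.** A reader might assume that neutral numbering is free. The documents give no costing, and bundle delivery now depends on the kit link.
- **Allocation by vendor software.** No defect in its generation is shown.

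None of these points supplies the missing masking statement.

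**Conclusion.** The point holds as a gap in protection, not as evidence of bias. The plan sends arm-linked kits to the vendor that generates the allocation and calls the primary outcome, and it does not mask that vendor's laboratory to arm. The access and data-sharing limits reduce the exposure but do not close it. The actual bias cannot be sized from the documents and may be nil. If 5-10% of treatment-arm events were missed at the 28% design rate, the distortion would be 1.4-2.8 points, 12-23% of the target. That is enough to justify an inexpensive safeguard. Sample size, alpha and power are unaffected. The plan should be changed here, but the finding does not invalidate the design.

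**What to change.** 1. Number all kits in one arm-neutral series, with identical return packaging.
2. Hold the kit-to-arm key at UIHC in EPIC and with the independent statistician, out of reach of RDB laboratory staff. The EPIC list already carries type of surgery and surgeon (VII.D.29), so the bundle can be delivered without an arm-linked kit.
3. Complete the blinding sentence in XI.1. State that culture, isolate-selection and clonal-relatedness calls are made and locked blind to arm, and that arm is joined afterwards for the feedback reports. State too that the VII.B.23 restriction keeps OR room and date from laboratory staff until lock. Neutral numbers alone would not be enough, because the platform also holds the allocation and counts events by arm.
4. Optionally, have the statistician generate the allocation.

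The cost is relabelling, a separate key and an access rule. Arm-specific feedback, which is part of the bundle, may be delayed until calls are locked. The documents give no turnaround time for clonal calls, so the sponsor should state the expected lag.
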